### **8.2.3. TETRAS-PS Upper Limb Tremor (Item 4) Total Score**

Item 4 of the TETRAS-PS represents upper limb tremor. Upper limb tremor is assessed during three maneuvers: forward outstretched posture, lateral “wing beating” posture, and kinetic (finger-chin-finger) testing. Each side of the body (right and left) is assessed and scored individually. The upper limb individual item score for each side of the body ranges from 0 to 4, with higher scores indicating more tremors. Derivation for the TETRAS-PS Upper Limb Tremor (Item 4) Total score is described in Section [6.1.8](#).

Assessments will be administered at Screening, Pre-dose, Day 1, Day 7, Day 14, and Day 21. Assessment results (scores) by local and central rater will be analyzed in the same way as described below for central rater score data. Observed values and change from baseline to all subsequent study visits in the upper limb subscale score will be summarized overall, by cohort (see Section [6.1.2](#)), and by study visit using descriptive statistics.

Additionally, tests of hypotheses comparing mean and median TETRAS-PS Upper Limb Tremor (Item 4) Total scores between baseline and subsequent study visits will be conducted using a 2-sided paired t-test and a Wilcoxon signed rank test, respectively. The null hypothesis is that the change from baseline in TETRAS-PS Upper Limb Tremor (Item 4) Total score to subsequent visit is 0 with a 2-sided alternative considering a difference in either direction (i.e., change from baseline not equal to 0, representing significant change in tremor).

As a supportive analysis, change from Screening to Baseline and change from Day 14 to Day 21 in each item score and in TETRAS-PS Upper Limb Tremor (Item 4) Total score will be summarized overall and by cohort (see Section [6.1.2](#)) using descriptive statistics.

A waterfall plot presenting mean change from baseline and 95% CI in TETRAS-PS Upper Limb Tremor (Item 4) Total Score by study visit will also be displayed. Additionally, a line graph of mean change from baseline and percent change from baseline will be displayed by study visit.

Commercially Confidential Information

Commercially Confidential Information

Commercially Confidential Information

### **8.2.9. Wearable Sensor (Kinesia)**

In addition to the assessment of efficacy via rating scales, treatment effect will be evaluated by measuring tremor with a sensor worn on the upper limb (right and left index fingers). These assessments will be conducted during the clinic visits and optionally at-home. The motion sensor uses three orthogonal accelerometers and three orthogonal gyroscopes to monitor three-dimensional motion. Data are then transmitted from the sensor to a computer using Bluetooth technology. These measures of three-dimensional motion for each maneuver are then converted to Kinesia scores. Each Kinesia score ranges from 0.0 to 4.0; higher scores indicate more severe tremor.

The wearable sensor measurements of upper limb tremor assessments will be completed in the clinic once at any time during the Screening visit and at two different times during the Pre-dose clinic visit. During the clinic visit on Days 1, 7 and 14, the wearable sensor measurements of upper limb tremor will be captured once, 2 to 4 hours following the in-clinic dose. During the Follow-up visit (Day 21), the wearable sensor measurements of upper limb tremor will be

completed at any time during the visit. In-clinic assessments will be obtained during the performance of 4 maneuvers:

1. extended arms posture,
2. wing-beating posture,
3. kinetic “finger-to-chin” movement, and
4. arm on table posture.

Two measurements at Pre-dose will be averaged and the means of 2 sets of measurements (mean of Kinesia score, mean amplitude, and mean frequency) will be used to represent Pre-dose values.

These assessments will be performed twice, once with the sensor on the left index finger and once with the sensor on the right index finger.

Observed values and change from baseline in the in-clinic wearable sensor measures of upper limb tremor severity, mean amplitude, and mean frequency will be summarized overall, by cohort (see Section 6.1.2), Commercially Confidential Information and study visit using descriptive statistics.

As a supportive analysis, change from Screening to Baseline and change from Day 14 to Day 21 in the in-clinic wearable sensor measures of upper limb tremor severity, mean amplitude, and mean frequency for the above maneuvers will also be summarized.

A waterfall plot presenting mean change from baseline and 95% CI in Wearable Sensor (Kinesia, in-clinic) measures by study visit will also be displayed.

Commercially Confidential Information

Commercially Confidential Information

## **9. Safety and Tolerability Analysis**

The primary endpoint of the study is the occurrence and severity of TEAEs.

Safety will be evaluated from reported AEs, serious AEs (SAEs), changes in clinical laboratory values, changes in vital signs, changes in orthostatic vital signs, 12-lead electrocardiograms (ECG), Columbia-Suicide Severity Rating Scale (C-SSRS), and physical and neurological examination results.

All safety analyses will be performed on the Safety population.

### **9.1. Adverse Events**

Any AE occurring after the date/time of informed consent signature but prior to the first dose of study medication (ie, occurring during the Screening and Baseline periods) will be listed. All AEs that occur after the first dose of study drug will be considered TEAEs. This includes any AEs that started or worsened (if present at baseline, increased in frequency or severity) after taking the first dose of the study drug. For AEs occurring on the date of first dose, if the time of onset is missing, the AE will be assumed to be treatment emergent.

All AEs will be coded using the MedDRA Version 21.1 or higher coding dictionary.

The causal relationship of the AE to the study drug is determined by the investigator as Not Related, Unlikely Related, Possibly Related, Probably Related, and Definitely Related. These will be mapped to Unrelated (*Not Related or Unlikely Related*) and Related (*Possibly Related, Probably Related, and Definitely Related*).

Adverse events severity grades are reported as mild, moderate, or severe.

Summaries of incidence rates (frequencies and percentages) of individual TEAEs will be presented by SOC, PT, and cohort. Such summaries will be displayed for all TEAEs, TEAEs by maximum severity, and TEAEs by relationship.

Each subject will be counted only once within each summation level (SOC and PT). If a subject experiences more than 1 TEAE within each summation level only the TEAE with the strongest relationship or the maximum severity, as appropriate, will be included in the summaries by subject for relationship and severity, respectively. If a particular event is missing the severity and/or relationship, then the strongest possible severity or relationship will be assumed for analysis (severity=severe, relationship = definitely related).

Incidence will be presented by descending frequency of SOC and PT within SOC, and then alphabetically within PT where the incidence is the same.

Missing and partially missing AE start and/or stop dates will be imputed, for the purpose of statistical analysis, according to the specifications described in Section 6.1.9.

Numbers of AEs will also be presented in these AE summary tables.

In the AE data listings, all AEs will be displayed. AEs that are treatment emergent will be flagged.

### **9.1.1. Adverse Events Leading to Withdrawal**

A summary of incidence rates (frequencies and percentages) of TEAEs leading to withdrawal of study drug or study discontinuation, by SOC, PT, and cohort will be prepared for the Safety population.

A data listing of AEs leading to withdrawal of study drug or study discontinuation will also be provided, displaying details of the event(s) captured on the CRF.

### **9.1.2. Deaths and Serious Adverse Events**

Any deaths that occur during the study will be listed.

SAEs will be listed and also tabulated by SOC, PT, and cohort.

## **9.2. Clinical Laboratory Evaluations**

Screening and safety laboratory tests will be performed at Screening, Pre-dose, Day 1, Day 7, Day 14, and at follow-up on Day 21. All laboratory test results will be summarized descriptively by study visit for the Safety Population overall and by cohort as both observed values and change from baseline values for each parameter. Categorical urinalysis results will be summarized using frequencies by study visit and cohort. Levels of composite biomarker panel for renal tubular injury will also be summarized by study visit and listed.

Shifts from baseline for clinical laboratory values below, within, or above the normal range will be provided for hematology and chemistry results by study visit. See Section 6.1.1 for the definition of baseline. Clinically significant abnormal findings will be reported as AEs. Abnormal laboratory results will be listed.

Pregnancy test results will be listed.

### 9.3. Vital Signs

Descriptive summaries of observed values and changes from baseline will be calculated for supine systolic blood pressure (SBP), standing SBP, supine diastolic blood pressure (DBP), standing DBP, supine heart rate (HR), standing HR, respiration rate, and oral temperature by study visit for the Safety Population overall and by cohort. Shifts from baseline for SBP, DBP, and HR values below, within, or above the normal range will be provided by study visit for the Safety Population overall and by cohort. Vital sign parameters outside the normal range will be flagged in the listings. The mean change from baseline in each parameter will also be plotted by study visit. Abnormal vital signs are as follows:

Commercially Confidential Information

- SBP >140 mmHg
- SBP <90 mmHg
- DBP >90 mmHg
- DBP <60 mmHg
- HR >100 bpm
- HR <60 bpm
- Respiration rate >20 breaths/min
- Respiration rate <12 breaths/min
- Oral temperature >99.1 °F/37.2 °C
- Oral temperature <97.8 °F/36.5 °C

Orthostatic vital signs (blood pressure and heart rate) will also be summarized by position and study visit and by cohort. During the Pre-dose visit, baseline orthostatic vital signs will include 3 separate measurements and the average of the 3 baseline orthostatic vital signs measurements will be used for comparison to all post-treatment measurements. The average HR, SBP, and DBP will be presented in the pre-dose baseline summaries and each of the individual measurements will be listed for that study visit.

Orthostatic hypotension will be defined as a reduction in systolic blood pressure of 20 mmHg or more and/or a reduction in diastolic blood pressure of 10 mmHg or more, for the standing measurement compared to the supine or semi-supine measurement. The frequency and percentage of subjects with orthostatic hypotension will also be presented by cohort. Any confirmed orthostatic hypotension or clinically significant measurements that are associated with clinical symptoms will be recorded as AEs. Orthostatic vital signs parameters outside the ranges specified above will be flagged in the listings.

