## **7.10       Orthostatic Vital Signs**

Orthostatic vital signs will be measured at Screening, Baseline, Day 1, Day 7, Day 14 and during the Follow-up visit.

During the Screening visit, orthostatic VS measurements will be done once, at any time during the visit.

During the Baseline/Pre-Dose visit, baseline orthostatic VS will include 3 separate measurements with each measurement of blood pressure and heart rate separated from the next by at least 15-20 minutes apart, to minimize the potential impact of biological variability of a single baseline measurement. The average of the 3 baseline orthostatic VS measurements will be used for comparison to all post-treatment measurements.

During Day 1, orthostatic VS measurements will be done twice, 2 to 4 hours following each in-clinic dose.

During Day 7 and Day 14 visits, orthostatic VS measurements will be done once, 2 to 4 hours following the in-clinic dose.

During the Follow-up visit, orthostatic VS measurements will be done once, at any time during the visit.

Orthostatic VS must be assessed using an appropriate device, and the arm position must be standardized for each subject. These measurements are to be taken in the same arm for the duration of the study. The position of the cuff on the arm should be in line with the heart with the arm lying next to the subject when semi-supine and should be in line with the heart at approximately a 45 degrees angle from horizontal for the standing measure.

In order to obtain orthostatic VS, the subjects will undergo the following procedures in sequential order:

1. The subject will rest in a supine or semi-supine position for at least 5 minutes.
2. After remaining supine or semi-supine for 5 minutes, one measurement of blood pressure and heart rate will be taken.
3. The subject will then be asked to sit on the edge of the bed/chair with feet on the floor (or with feet dangling from the bed/chair depending on the height of the bed/chair) for approximately 30 seconds.
4. The person performing the assessment will then ask the question, “Are you ready to stand?”
  - If the subject responds in the affirmative, the subject will proceed to stand and then be asked to remain standing for 2 minutes. After standing for 2 minutes, blood pressure and heart rate will be recorded.

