## 4. Statistical Analysis and Reporting

### 4.1. Introduction

Data processing, tabulation of descriptive statistics, calculation of inferential statistics, and graphical representations will be performed primarily using SAS (release 9.4 or higher).

Commercially Confidential Information If the use of other software is warranted, the final statistical methodology report will detail what software was used for what purposes.

Continuous (quantitative) variable summaries will include the number of subjects (n) with non-missing values, mean, standard deviation (SD), median, minimum, and maximum.

Categorical (qualitative) variable summaries will include the frequency and percentage of subjects who are in the particular category for each possible value. In general, the denominator for the percentage calculation will be based upon the total number of subjects in the study population, unless otherwise specified. The denominator for by-visit displays will be the number of subjects in the relevant study population with non-missing data at each visit. If there is any missing value for a categorical analysis, a “Missing” category will be displayed as the last category in the table for the variable.

For weight, height, CCI one decimal place will be used for all summary statistics. For all other summaries, the minimum and maximum will be reported with the same degree of precision (i.e., the same number of decimal places) as the observed data. Measures of location (mean and median) and confidence interval boundaries will be reported to 1 degree of precision more than the observed data, up to 3 decimal places. Measures of spread (SD) will be reported to 2 degrees of precision more than the observed data, up to 3 decimal places.

Percentages will be presented to 1 decimal place, unless otherwise specified. Percentages equaling 0 or 100 will be displayed with no decimal places or percentage symbols.

Fractional numeric values will be presented with a zero to the left of the decimal point (for example, 0.12 – 0.30).

Unless otherwise indicated, all statistical tests will be conducted at the 0.05 significance level using 2-tailed tests, and *P* values will be reported. Corresponding 95% confidence intervals (CIs) will be presented for statistical tests, where applicable.

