**Same shell as Table 14.3.5.1.1**

**Programming note:** Visits include Screening, Baseline, Day 1, Day 7 Post-Dose, Day 14 Post-Dose, and Day 21; parameters include Standing Systolic Blood Pressure (mmHg), Supine Systolic Blood Pressure (mmHg), Supine Heart Rate (bpm), Standing Heart Rate (bpm), Standing Diastolic Blood Pressure (mmHg), and Supine Diastolic Blood Pressure (mmHg); SOURCE: Listing 16.2.8.3.1, Listing 16.2.8.3.2.

Table 14.3.6.1.4  
Shift from Baseline in Orthostatic Vital Signs by Study Visit  
Safety Population

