**Same shell as Table 14.3.5.1.2**

**Programming note:** Visits include Screening, Baseline, Day 1, Day 7 Post-Dose, Day 14 Post-Dose, and Day 21; parameters include Standing Systolic Blood Pressure (mmHg), Supine Systolic Blood Pressure (mmHg), Supine Heart Rate (bpm), Standing Heart Rate (bpm), Standing Diastolic Blood Pressure (mmHg), and Supine Diastolic Blood Pressure (mmHg); Update footnote to SOURCE: Listing 16.2.8.3.1, Listing 16.2.8.3.2

Table 14.3.6.1.5  
Summary of Orthostatic Vital Signs Shift from Baseline Categories by Study Visit  
Safety Population

Study Visit Shift Category	Cohort-1			Cohort-2		
	SBP [1] (N=XX) n (%)	DBP [1] (N=XX) n (%)	HR [1] (N=XX) n (%)	SBP [1] (N=XX) n (%)	DBP [1] (N=XX) n (%)	HR [1] (N=XX)
Day 7						
Shifted	XX (XX.X%)	XX (XX.X%)	XX (XX.X%)	XX (XX.X%)	XX (XX.X%)	XX (XX.X%)
Unshifted	XX (XX.X%)	XX (XX.X%)	XX (XX.X%)	XX (XX.X%)	XX (XX.X%)	XX (XX.X%)
Missing	XX (XX.X%)	XX (XX.X%)	XX (XX.X%)	XX (XX.X%)	XX (XX.X%)	XX (XX.X%)
Day 14						
Shifted	XX (XX.X%)	XX (XX.X%)	XX (XX.X%)	XX (XX.X%)	XX (XX.X%)	XX (XX.X%)
Unshifted	XX (XX.X%)	XX (XX.X%)	XX (XX.X%)	XX (XX.X%)	XX (XX.X%)	XX (XX.X%)
Missing	XX (XX.X%)	XX (XX.X%)	XX (XX.X%)	XX (XX.X%)	XX (XX.X%)	XX (XX.X%)
Day 21						
Shifted	XX (XX.X%)	XX (XX.X%)	XX (XX.X%)	XX (XX.X%)	XX (XX.X%)	XX (XX.X%)
Unshifted	XX (XX.X%)	XX (XX.X%)	XX (XX.X%)	XX (XX.X%)	XX (XX.X%)	XX (XX.X%)
Missing	XX (XX.X%)	XX (XX.X%)	XX (XX.X%)	XX (XX.X%)	XX (XX.X%)	XX (XX.X%)

Abbreviations: DBP= diastolic blood pressure (mmHg); HR = heart rate (bpm); SBP = systolic blood pressure (mmHg).

Note: Percentages are n/Number of subjects in the Safety Population and respective Protocol Amendment \* 100. Shift status is defined as a reduction in SBP of 20 mmHg or more, and/or a reduction in DBP of 10 mmHg or more, and/or an increase in heart rate >20 beats/min for the standing measurement compared to the supine or semi-supine measurement.

[1] The baseline value for each variable is the last observation recorded prior to the first dose of treatment.

SOURCE: Listing 16.2.8.3.2

**Programming note:** Repeat table for Overall.

Table 14.3.6.1.6  
Summary of Orthostatic Hypotension by Study Visit  
Safety Population

Study Visit Category	Cohort-1 (N=XX) n (%)	Cohort-2 (N=XX) n (%)	Overall (N=XX) n (%)
Baseline [1]			
Reduction of SBP of 20 mmHg or more	XX (XX.X%)	XX (XX.X%)	XX (XX.X%)
Reduction of DBP of 10 mmHg or more	XX (XX.X%)	XX (XX.X%)	XX (XX.X%)
Day 7 Post-Dose			

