Reduction of SBP of 20 mmHg or more	XX (XX.X%)	XX (XX.X%)	XX (XX.X%)
Reduction of DBP of 10 mmHg or more	XX (XX.X%)	XX (XX.X%)	XX (XX.X%)
Day 14 Post-Dose			
Reduction of SBP of 20 mmHg or more	XX (XX.X%)	XX (XX.X%)	XX (XX.X%)
Reduction of DBP of 10 mmHg or more	XX (XX.X%)	XX (XX.X%)	XX (XX.X%)
Day 21			
Reduction of SBP of 20 mmHg or more	XX (XX.X%)	XX (XX.X%)	XX (XX.X%)
Reduction of DBP of 10 mmHg or more	XX (XX.X%)	XX (XX.X%)	XX (XX.X%)

Abbreviations: DBP = diastolic blood pressure; SBP= systolic blood pressure.

Note: Percentages are n/Number of subjects in the Safety Population and respective Protocol Amendment\*100. Orthostatic hypotension is defined as a reduction in SBP of 20 mmHg or more, and/or a reduction in DBP of 10 mmHg or more, for the standing measurement compared to the supine or semi-supine measurement.

[1] The average of the 3 baseline orthostatic vital signs measurements will be used for comparison to all post-treatment measurements.

SOURCE: Listing 16.2.8.3.2

Table 14.3.6.2.1  
Summary of 12-Lead Electrocardiogram by Study Visit  
Safety Population

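### No SAP table gives the orthostatic hypotension count (SBP and/or DBP) promised in SAP 9.3, and the two tables that count orthostatic drops have no Day 1 row

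*SAP*

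**What the plan says.** **The promise.** SAP 9.3 defines OH by comparing the standing reading with the supine or semi-supine one. A subject qualifies on the systolic criterion, the diastolic criterion or both. It then commits to a count: "The frequency and percentage of subjects with orthostatic hypotension will also be presented by cohort".

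**The measurements.** Protocol 7.10 states: "During Day 1, orthostatic VS measurements will be done twice, 2 to 4 hours following each in-clinic dose". Days 7, 14 and 21 have one reading each. On baseline it says: "The average of the 3 baseline orthostatic VS measurements will be used for comparison to all post-treatment measurements". SAP 9.3 repeats this.

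**The shells (SAP 14.2).**
- Table 14.3.6.1.3 summarises values by position. Its programming note reads: "Visits include Screening, Baseline, Day 1, Day 7 Post-Dose, Day 14 Post-Dose, and Day 21". Table 14.3.6.1.4, which shows low/normal/high shifts by position, has the same visit list.
- Table 14.3.6.1.5 shows Days 7, 14 and 21 in separate SBP, DBP and HR columns. One definition covers all three columns. It starts with the two pressure criteria and ends "and/or an increase in heart rate >20 beats/min for the standing measurement compared to the supine or semi-supine measurement".
- Table 14.3.6.1.6 shows Baseline, Day 7, Day 14 and Day 21. Each visit has a row "Reduction of SBP of 20 mmHg or more" and a matching DBP row. The and/or definition stands only in its footnote.

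**The denominator.** Both counting tables carry the footnote "Percentages are n/Number of subjects in the Safety Population and respective Protocol Amendment". SAP 4.1 says: "The denominator for by-visit displays will be the number of subjects in the relevant study population with non-missing data at each visit".

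**The concern.** Safety is the primary objective, and Day 1 is the first exposure to the drug. Programmed as written, the shells would give an OH table that omits both Day 1 readings and never states how many subjects had OH. A reader of the tables would have to count by hand from the listing.

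The adverse event tables do not fully fill this gap. Protocol 7.10 leaves a repeat measurement to the Investigator's discretion and sends confirmed or symptomatic findings to adverse event reporting. An asymptomatic drop that is not repeated may therefore appear only in the listing.

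**Working it through.** The documents give no expected OH rate, and SAP 3.2 reports no power analysis, so there is no stated figure to reproduce. The check compares the measurement schedule with the shells and then asks whether the printed rows can yield the promised count.

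**1. Coverage of readings** (protocol 7.10, per completer)

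| Visit | Readings | In 14.3.6.1.5 | In 14.3.6.1.6 |
|---|---|---|---|
| Day 1 | 2 | no | no |
| Day 7 | 1 | yes | yes |
| Day 14 | 1 | yes | yes |
| Day 21 | 1 | yes | yes |

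On treatment: 2 + 1 + 1 = 4 readings, of which 2 are omitted (2/4 = 50%). All post-dose readings including Day 21: 5, of which 2 are omitted (2/5 = 40%).

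This does not look like shorthand in the shells. The only programming note on 14.3.6.1.5 asks for a repeat for Overall, and 14.3.6.1.6 has none. Where other shells are abbreviated, such as the ECG tables, a note says which visits to continue with.

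**2. Can the combined count be derived from Table 14.3.6.1.6?** Let a subjects meet the SBP criterion and b the DBP criterion, out of N. The number with OH lies between max(a, b) and min(a + b, N). It is exact only if a or b is zero. With N = 30 (the enrolment ceiling in SAP 3.2) and assumed counts:

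| a | b | Subjects with OH | Percent |
|---|---|---|---|
| 1 | 1 | 1 to 2 | 3.3 to 6.7 |
| 2 | 2 | 2 to 4 | 6.7 to 13.3 |
| 2 | 3 | 3 to 5 | 10.0 to 16.7 |
| 4 | 6 | 6 to 10 | 20.0 to 33.3 |

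**3. Does Table 14.3.6.1.5 supply it?** There are two ways to read that shell. If each column applies its own criterion, the SBP and DBP columns are again separate counts, so the bounds in step 2 apply. If the definition is applied as worded, every column shows one composite that also counts subjects with only a heart-rate rise, which is not OH under SAP 9.3. Neither reading gives the promised count.

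**4. Denominator.** Suppose 2 subjects have a drop. Over 30 in the Safety Population that is 2/30 = 6.7%. If 28 or 24 have a reading (assumed), SAP 4.1 gives 2/28 = 7.1% or 2/24 = 8.3%. The two rules differ, but not by much.

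**5. A separate, minor mismatch.** SAP 9.3 and the footnote to Table 14.3.6.1.2 flag heart rate below 60 bpm and temperature above 99.1 °F or below 97.8 °F. The footnote to Listing 16.2.8.3.1 uses below 50 bpm, above 99.5 °F and below 97 °F.

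**The case against.** **No stated commitment on Day 1.** SAP 9.3 promises the count by cohort and names no visits. Some other categorical shells also start at Day 7, for example the hematology shift table. This is fair: the documents do not support saying that the SAP breaks an explicit promise to tabulate Day 1. The gap rests on three other things: the title of Table 14.3.6.1.6 says it is by study visit, the schedule takes two Day 1 readings, and the baseline is to be compared with all post-treatment measurements. The sister tables that name Day 1 support this reading. The missing combined count does not depend on the choice of visits.

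**Table 14.3.6.1.5 is not the OH table.** Its title concerns shift categories, and the natural reading is one criterion per column. That is probably what was meant, but its definition does not say so. It also leaves Table 14.3.6.1.6 as the only place for the count.

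**The denominator is not specific to OH.** The same Safety Population footnote sits on Tables 14.3.5.1.2, 14.3.5.3.3, 14.3.6.2.2 and 14.3.6.2.3. This stands. Changing only the two orthostatic tables would create a new inconsistency.

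**Missing data are already handled.** A reader might infer that nobody could tell how many subjects were measured. SAP 4.1, 13 and 14.1 call for a Missing category wherever data are missing, and Table 14.3.6.1.3 prints n by visit, so a close denominator is available. A reader might also infer that an unmeasured cohort would print as zero, but SAP 13 says to leave the statistics blank when there are no subjects at a time point. An n row in the OH table is still the clearer display.

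**Conclusion.** The point holds as a modest tabulation defect. The count of subjects with OH as SAP 9.3 defines it appears in no table. Both tables that count orthostatic drops omit Day 1, which is 2 of the 4 on-treatment readings or 2 of the 5 post-dose readings under the current protocol. These fractions follow from the schedule. The percentages in the working are illustrations with assumed counts.

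A reader might go further and infer that Day 1 orthostatic data are lost or that OH would go unreported. The documents do not support that. The readings are collected, Listing 16.2.8.3.2 has an OH flag, and confirmed or symptomatic OH is recorded as an adverse event and so feeds the primary endpoint. Nor is the averaged baseline hidden in Table 14.3.6.1.6, since the footnote attached to its Baseline row refers to the average of three readings.

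The orthostatic schedule for Cohort-1 is not in the documents, so it is not known whether that cohort has both Day 1 readings.

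**What to change.** 1. Add rows for Day 1 after dose 1 and Day 1 after dose 2, where measured, to Tables 14.3.6.1.5 and 14.3.6.1.6.
2. In Table 14.3.6.1.6, add at each visit a row for OH (SBP and/or DBP) and a row for the number of subjects with a reading. Keep the separate SBP and DBP rows.
3. In Table 14.3.6.1.5, state that the SBP, DBP and HR columns each apply their own criterion.
4. Use the non-missing by-visit denominator of SAP 4.1 in both tables and, for consistency, in the sibling by-visit safety shells. Show the Missing row of Table 14.3.6.1.5 as a count only.
5. Separately, reconcile the abnormal heart-rate and temperature limits in SAP 9.3 and Table 14.3.6.1.2 with the footnote to Listing 16.2.8.3.1.

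The cost is edits to SAP shells and footnotes, plus the matching programming. No new data are needed, and the protocol-defined baseline stays as it is. Day 1 rows may be empty or partly empty for Cohort-1.
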